**Aim 1: Identify baseline prevalence of psychotic disorders and psychosis-risk syndromes within the JJ system.** We will calculate the percentage of youth who screen positive on the MAYSI-2 Thought Disturbance subscale and/or *PQ-B* over the 2-year period of the study. We will also calculate mean, median, and range of DUI/DUP in months, for both sub- and full- threshold psychosis. Correlations and regression techniques will be used to explore the relation between attenuated psychosis (both individual symptoms and syndromes) and co-occurring symptoms (BPM symptomatology; MINI symptoms and diagnoses). Prevalence estimates will make use of a weighted sample that takes into account the selection probability for SIPS evaluation given MAYSI-2 and *PQ-B* results, so that our results are generalizable back to the population of JJS youth. We will also examine the utility of the MAYSI-2 Thought Disturbance subscale and *PQ-B* as screeners for psychosis-spectrum syndromes and disorders by determining the criterion-related validity (e.g., sensitivity, specificity, positive and negative predictive value) of number of items endorsed for predicting psychosis risk, as confirmed by clinical interview with the SIPS, as well as compare the two screens. This analysis will also use the weighted data from the MAYSI-2 and *PQ-B* and SIPS evaluation sample, and logistic regression procedures.

**Aim 2A: Examine whether an enhanced referral procedure results in higher proportion of completed referrals to the CSC compared to standard referral procedures** by calculating the proportion of completed referrals in Phase I, standard care, versus Phase II, when an enhanced referral/linkage to care procedure is instituted in JJS. An 80% linkage will be considered a success, and reflects the expected linkage proportion in Phase II. The probability of linkage will be contrasted across phases using logistic regression procedures.

**Aim 2B: Identify implementation and service level factors that promote/hinder linkage to the CSC.** Feasibility and Penetration, the number and percentage of JID personnel trained and consistency (% of time) using the enhanced referral protocol will be calculated with descriptive statistics. A rate of 80% will be the benchmark. Efficiency will be rated by the number of text message and phone contacts necessary to complete the referral to the CSC. A benchmark of two contacts will be considered an indicator of efficiency. Equity of enhanced referral protocol fidelity and treatment linkage across gender, race, and ethnicity will be compared across Phase I (Standard Care) and Phase II (Enhanced Referral/Linkage to Care condition), as well as cross-sectionally in the Enhanced Referral/Linkage to Care condition only, using cross-tabulation approaches. Acceptability. JJS staff perceived roles in screening and referral will be reported in percentages based on qualitative interviews as well as by mean, median, and range of scores on the Attitudes toward Mental Health

Screening measure. A total of 80% of the JID personnel scoring within one standard deviation of the mean on this measure based on the literature will be the benchmark.

**Aim 3A: Investigate client level factors at follow-up.** Attitudes about CSC referrals. These analyses follow the qualitative interview procedure described above. Rates of treatment initiation/retention in CSC services or other mental health care. Percentages of CSC participation will be calculated with 80% set as the benchmark as will other types of mental health care as rated on the CASA. For those already in mental health care at the time of enrollment, percentages of consultation to the CSC will be calculated, as will the types of treatment received and frequency/intensity of the services. Treatment barriers and motivation. Scores on the *Motivation for Youth's Treatment Scale* and the *Barriers to Treatment Participation Scale* will be analyzed using a paired t-test to determine any changes in these measures from baseline to three month follow-up. Treatment Satisfaction. These analyses follow the qualitative interview procedure described above.

**Aim 3B: Investigate mental health indicators at follow-up.** Psychosis-spectrum symptoms will be assessed on the SIPS (which will also allow examination of the effects of the intervention on DUP, DUI, and functioning) and other clinical outcomes on the subscales of the BPM. The goal of this aim is to obtain a reasonably precise estimate of the standard deviation for the outcome variables, and pre-post correlations of outcome variables, which are essential statistics for powering a definitive trial. Following Leon and colleagues (2011) and Kraemer and colleagues (2006), our goal is not to obtain a preliminary estimate of the treatment effect size, but as per Teare and colleagues (2014), the size of the pilot we propose is sufficient to obtain sufficiently precise estimates of key variance and covariance parameters necessary to design a definitive trial. Our approach will be to conduct an analysis consistent with the testing of the hypothesis that JJS youth enrolled in the Enhanced Referral/Linkage to Care condition will have fewer psychosis-spectrum symptoms and other clinical outcomes at 3 month follow-up relative to youth in the baseline control.

The main outcomes are individual and total symptom scores (reflecting intensity, interference, and conviction) as well as diagnosis (i.e., low-risk, high-risk, or psychosis) and illness trajectory (i.e. progression, persistence, and partial or full remission) from the SIPS. We will also examine treatment attendance, motivation for treatment, and treatment barrier reduction. The analysis framework will be linear regression, with psychosis-spectrum symptoms as the outcome and Enhanced Referral/Linkage to Care condition as the main predictor. In a randomized design, we would be certain that randomization introduced control for measured and unmeasured factors. In the baseline control design, we cannot be sure that secular trends might not cause different kinds of adolescents to become referred to JJ and/or influence their responses to questions about psychotic-like symptoms. For this reason, we will control for a select set of *a priori* identified confounding variables (sex, gender, race, ethnicity, and age), past history of psychosis-spectrum symptoms, and ongoing mental health treatment at the time of enrollment. The sign and standard error of the enhanced referral/linkage to care condition describes the magnitude and significance of the treatment effect at the threshold level of the screen. For the purposes of this pilot, key outcome parameters are the standard deviation of the SIPS positive symptom scores, the pre-post correlation of the SIPS scores, and the overall  $R^2$  in follow-up SIPS scores given pre-specified covariates. These parameters would be necessary to estimate the sample size requirements for a definitive trial.

**Aim 3C. Relationship between service mechanisms (treatment linkage and attendance) and psychotic symptoms/DUP.** Correlation and regression techniques will be used to examine how use of services over the 3-month study period is related to change in psychosis-spectrum symptoms as assessed by the SIPS as well as general symptomatology, as assessed by the BPM.

**Exploratory analyses.** In exploratory analyses, we will also assess potential moderators of the Enhanced Referral protocol effect. We are particularly interested in whether or not the effect of the Enhanced Referral protocol varies by sex, gender, race, ethnicity, and socioeconomic status, as well as service level factors, i.e., fidelity of JID and CSC staff to the referral process. These exploratory analyses will be accomplished by repeating our main analysis models, described above, but including main and interaction effects of selected potential moderators with study phase. Inference will be based on effect size statistics for interaction effects and used as hypothesis generating results for future studies.

**Power:** As mentioned above, per simulation studies conducted by Teare and colleagues (2014), a total sample size of 60 is sufficient to obtain reasonably precise estimates of key design parameters necessary to power a definitive trial with continuous outcomes. Therefore, our total sample of 140 at baseline and 110 at 3 month follow-up should be sufficient to conduct a simulation study and determine power for a definitive trial.

**Timeline: Months 1 - 2:** Start-up; **Months 3- 14:** 12 months of baseline data collection on Standard Care condition (baseline control); **Months 6 - 17:** 3 month follow-up on Standard Care condition; **Months 18 - 19:** Training of JID intake workers in Enhanced Referral/Linkage to Care protocol; **Months 20 - 31:** 12 months of data collection on the Enhanced Referral/Linkage to Care condition; **Months 23 – 34:** 3 month follow-up on Enhanced Referral/Linkage to Care protocol; **Months 35 - 36:** Analyze data and prepare manuscript.

**Future research.** As stated in the FOA, this R34 planning grant proposes “the developmental work to be performed that enhances the probability of success in a larger study” and “develops and refines the research strategies to be utilized in the subsequent large-scale study....as well as close gaps in the pathway to specialty

FEP care". If successful, this planning grant will set the stage for a Type III Effectiveness-Implementation design to test this implementation strategy while also collecting data on the Enhanced Referral protocol's effect on linkage to CSC level care, DUP, and psychosis-spectrum symptoms.

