The current study will be conducted in the Rhode Island JJS in which all youth receive a mental health screen (Massachusetts Youth Screening Instrument – 2nd Ed; MAYS-2). All youth *will also be screened with the Prodromal Questionnaire – Brief Version (PQ-B)*. If they screen in on either the MAYS-2 or the PQ-B, they will be given referral information for CSC services by JJS staff. They will also be offered the opportunity to participate in the research assessment, regardless of whether they pursue the CSC referral, which involves the Structured Interview for Psychosis-risk Syndromes [SIPS] and other measures to thoroughly assess history of psychotic symptoms, comorbid difficulties, and mental health care engagement. A comparison sample of youth who do not screen positive on both the MAYS-2 Thought Disturbance subscale and PQ-B will also be assessed with the SIPS to determine accuracy of the MAYS-2 and PQ-B in the identification of psychosis-risk. During the first part (12 months) of the study, JJS staff will follow standard procedures in referring youth to the state CSC. In the second part of the study (also 12 months), JJS staff will be instructed in the enhanced referral/linkage to care protocol, including a “warm hand-off” where referrals will be put in direct and immediate contact with CSC staff. CSC staff will also be trained in procedures to increase the likelihood of follow through with the referral to the CSC. The research team will conduct 3 month follow-up qualitative interviews and quantitative assessments regarding referral pathways, bottlenecks and gaps in care, youth psychiatric symptoms, and JJS contacts. The following specific aims, mapped to the **four stated goals of PAR 16- 264**, will be examined:

**Aim 1A: Identify baseline rates of psychosis-spectrum disorders within the JJS** by exploring the occurrence of psychotic disorders and psychosis-risk syndromes as identified through clinical interview with the SIPS. **1B: Examine Duration of Illness (DUI)** for sub- and DUP for full- threshold psychosis, in the JJS population based on SIPS interview data. **1C: Examine the accuracy (i.e., sensitivity, specificity) of the MAYS-2 and PQ-B** in identifying youth with psychosis-spectrum disorders, as defined by the SIPS.

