The use of brief psychosis-risk screening tools has the potential to conveniently identify individuals who may benefit from a thorough interview-based evaluation. Several screening tools have been developed and validated among help-seeking clients in the context of psychosis-risk clinics, however, given constraints related to implementation of new, specialized measures within community settings, it is likely that a more feasible and acceptable approach to screening would include the use of key items within a broad measure of mental health concerns. Key-item screening is defined as the use of a limited number of specific items across

a wide range of clinical domains to, 1) assess risk, and 2) prompt further probing within specific areas of concern. If a client endorses a key item, the clinician follows up with additional questionnaires and/or clinical interviewing. Many non-specific mental health questionnaires have been developed to screen across multiple diagnostic categories, and success in the prediction of certain concerns (e.g., anxiety) has been demonstrated. The validity of key items to screen for psychosis risk, however, has never been systematically examined as a means to facilitate more widely adopted intervention for early psychosis.

**Youth in the Juvenile Justice System.** One high risk group that receives relatively little attention in the literature with respect to identification and referral to treatment for psychotic symptoms is youth involved in Juvenile Justice (JJ). This study will focus specifically on court-involved, but non-incarcerated (CINI) juveniles, who comprise approximately two-thirds of the JJ population seen in the Juvenile Justice System (JJS). In Rhode Island, these youth, typically ranging in age from 11-18, have their first contact with the JJS in the Rhode Island Family Court (RIFC) Juvenile Intake Department (JID), a diversion based program for first-time offending youth. Most first-time offending, CINI juvenile offenders are diverted through monitoring (typically 90 days) by a juvenile intake coordinator who makes various referrals (e.g., substance abuse treatment, mental health evaluation) and closely monitors adherence with the caveat that intake requirements must be completed to avoid further JJ involvement (see letter of support from Chief Judge [name]).

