**Linkage to treatment among JJ youth.** In RI, the majority of youth (67%) who made their first contact with the JJS fell into the caution or warning range of at least one mental health subscale of the Massachusetts Youth Screening Instrument- Second Edition (MAYSI-2) with 40% flagging on at least 2 subscales. For many youth, the JJS is the first point of contact for mental health support and often their only access to these services. CINI youth who endorse recent psychiatric symptoms on screening tools generally do not have immediate access to a medical or mental health provider for services. For example, Burke and colleagues (2015) found that 74% of youth who made their first contact with the JJS had a psychiatric disorder, yet only 20% reported receipt of mental health services at follow-up assessments. In another study, youth in the JJS had the lowest rates of mental health treatment utilization in a large sample of adolescents who received services in at least one public sector of care, e.g., alcohol and drug services, child welfare, etc. Lack of access to needed mental health services among JJ youth, may increase risk for a range of future psychopathology, including psychotic symptoms. *Connecting JJ youth to care is a priority of this application.*

At the RIFC JID, evidenced-based screening measures, including the MAYSI-2, were implemented in 2014 to screen CINI youth for mental health and substance use issues. To date, 11% of these youth flag in the caution or warning range on the MAYSI-2 Thought Disturbance subscale. Unless they are floridly psychotic and require emergency care, the overwhelming majority of these CINI youth return home with referral information to a community mental health clinic or, at best, a future mental health appointment with a poor rate (48-62%) of treatment uptake in the RI community. The National Center for Mental Health and Juvenile Justice (NCMHJJ) Blueprint for Change goals include access to mental health treatment for all youth who endorse mental health symptoms indicating risk for a possible crisis or self-harm^34, a frequent concern of individuals with psychotic symptoms.

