
The assembled research team collectively brings expertise in the assessment of adolescents with a broad range of psychopathology, including psychosis-spectrum disorders, experience in conducting community-based research, and experience in improving assessment and referral within the juvenile justice system.

**Participants.** JJS offenders, ages 12- 17, will be eligible for enrollment with the following criteria: 1) legal guardian available to consent for juvenile’s participation, and adolescent assents to participate; 2) juvenile is English speaking; parents may be Spanish-speaking because we will have Spanish-speaking research staff and interpreter services available; and 3) juvenile flags positive on the MAYSI-2 Thought Disturbance subscale or the PQ-B. Exclusion criteria include: 1) observable developmental delays that would interfere with obtaining assent and/or accurate assessment, and 2) juvenile meets hospital level of care for imminent risk due to severity of symptoms, in which case they will be transported to Emergency Department per existing JID procedures. In addition, we will collect a comparison sample (n = 70) meeting these same inclusion/exclusion criteria with the exception that they will screen negative on the MAYSI- 2 Thought Disturbance subscale and PQ-B. This subgroup will be used in analyses exploring the sensitivity/specificity of the MAYSI-2 Thought Disturbance subscale and PQ-B.. The MAYSI-2 is a 52-item self-report measure for ages 12-17 that screens for current MH symptoms. The Thought Disturbance Subscale consists of 5 items, 4 of which refer to altered perceptions of reality and the fifth to de-realization. The developers do not recommend use of the subscale with girls. *The PQ-B, a 21 item measure for both males and females, with an 8th grade reading level and takes 3-4 minutes to complete. In a sample of 141 adolescents and young adults referred for assessment to prodromal research centers, the instrument achieved specificity of 0.68 and sensitivity of 0.88 with regard to SIPS diagnoses using a cutoff distress score threshold of six or greater on the weighted distress measure. A recent review indicated sensitivity ranging from .70-.97 across different samples*.

**Racial and ethnic minority considerations.** Consistent with 2016 RIFC statistics, ethnic representation will be approximately 18% Hispanic and racial representation will be about 22% African American or Black

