**Estimated sample size and retention rates.** In 2016, the RIFC handled offenses for 2,634 juveniles of whom 764 (29%) were female and 2,581 (98%) who were in the 12-17 year old age range. The JID, for example, typically screens more than 900 juveniles per year and, of those youth who are screened, approximately 11% (N= 99) flag for thought disturbance. With a conservative enrollment rate of 70%, and 12 months of enrollment in both the baseline control (n = approximately 100 positive screens) and experimental intervention condition (n = approximately 100 positive screens), we would be able to meet our projected enrollment goals for both baseline standard care (n = 70) and enhanced referral (n=70) conditions. Using a conservative follow-up rate of 80% of the 140 enrolled and retained participants, approximately 55 families in both the baseline control and experimental condition are expected to complete the 3-month follow-up. In addition, we will recruit 70 youth in Phase I and Phase II who do not screen positive on the MAYSI-2 or PQ-B in order to conduct the sensitivity/specificity analyses. These projections are feasible given our excellent working relationship with the Rhode Island JJS including the RIFC and prior experience recruiting from the JID (see RIFC Chief Judge Letter of Support). Co-I [name] collaborated on a 24-month longitudinal epidemiological study of first-time CINI offenders at the RIFC and she successfully recruited the entire sample of 400 first-time offending CINI youth (DA034538). Co-I [name] is also currently recruiting at the RIFC JID for a baseline sample of suicidal CINI youth for her NIMH K23 Mentored Career Award. PI [name] also successfully established a referral system from RIFC to two completed grants, NIAAA (AA017659) and NIDA (DA0029871) trials for youth with substance use-related court involvement.

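### Aim 1 prevalence cannot be weighted to all juvenile justice youth, because acutely ill youth and youth outside JID intake are never sampled

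*Combined protocol and SAP*

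**What the plan says.** Specific Aims sets Aim 1A as "Identify baseline rates of psychosis-spectrum disorders within the JJS". Under the Data Analysis Plan (Aim 1), prevalence is estimated from a sample weighted by each youth's chance of a SIPS interview, which is taken to depend on the two screens alone. The stated purpose of this weighting is "so that our results are generalizable back to the population of JJS youth". The same weighted data feed the sensitivity and specificity analysis.

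Three other places limit who can be sampled:

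- **Participants** excludes a youth if the "juvenile meets hospital level of care for imminent risk due to severity of symptoms"; such youth go to the Emergency Department. The comparison sample is recruited "meeting these same inclusion/exclusion criteria with the exception that they will screen negative", so the exclusion applies there too.
- **Linkage to treatment among JJ youth** describes usual practice. "Unless they are floridly psychotic and require emergency care", nearly all of these youth go home with a referral or, at best, a later appointment.
- **Youth in the Juvenile Justice System** restricts the study to court-involved, non-incarcerated youth, about two-thirds of the juvenile justice population. They first meet the system at the JID, "a diversion based program for first-time offending youth". **Estimated sample size and retention rates** says the JID "typically screens more than 900 juveniles per year", against 2,634 juveniles handled by the court in 2016.

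No section plans to count or classify the excluded youth, to weight to the wider system, or to run a sensitivity analysis for either group.

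**The concern.** Inverse-probability weights correct for unequal sampling among youth who could have been sampled. They do nothing for youth whose probability is zero. One of the two zero-probability groups is defined by severity of symptoms, which is close to what Aim 1A measures, and the background text suggests that the clearest psychotic cases take that route. A reader of the results would take the weighted figure as a rate for the whole system when it describes a narrower and less acute group. The duration of untreated psychosis in Aim 1B may omit the most acute cases for the same reason, and the screening-accuracy analysis inherits the same truncated sample.

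**Working it through.** **1. The plan's own figures.** 0.11 × 900 = 99 positive screens a year. 0.70 × 99 = 69.3, and 0.70 × 100 = 70 enrolled per phase. 0.80 × 70 = 56 against the stated 55 or so per phase, and 0.80 × 140 = 112 against the stated 110. These reproduce. The plan gives no expected prevalence or precision for Aim 1A.

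**2. The implied weights over two years.** About 1,800 are screened, with 198 positive and 1,602 negative. The 11% is the MAYSI-2 rate alone; PQ-B positives would raise it.

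- Positives: 140/198 = 0.71, weight 1.41.
- Negatives: 70/1,602 = 0.044, weight 22.9. If 70 negatives are taken in each phase, 140/1,602 = 0.087, weight 11.4.
- Hospital-level exclusions and youth outside the JID: probability 0, so no finite weight exists.

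**3. Effect of the acute exclusion (illustration).** Assumptions: true full-threshold prevalence among screened youth is 3%, so D = 54 cases among N = 1,800; positives P = 198; a fraction f of cases and m of non-cases is excluded, all of them screen-positive; cases among positives Dp = 54 (all detected) or 0.88 × 54 = 47.5 (the PQ-B sensitivity quoted in Participants).

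Excluded: E = fD + m(N − D). Weighted estimate = [P × (Dp − fD)/(P − E) + (D − Dp)]/N.

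Example with f = 25%, m = 0, Dp = 54: E = 13.5; 198 × 40.5/184.5 = 43.5; 43.5/1,800 = 2.41%.

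| f (cases excluded) | m (non-cases excluded) | Prevalence among eligible | Weighted estimate |
|---|---|---|---|
| 10% | 0 | 2.71% | 2.77–2.78% |
| 25% | 0 | 2.27% | 2.39–2.41% |
| 50% | 0 | 1.52% | 1.68–1.74% |
| 10% | 1% | 2.73% | 3.01–3.05% |

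In the first three rows weighting closes little of the gap to 3%. In the last row there is no under-count.

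**4. When the direction reverses.** The estimate is low only if psychosis is commoner among excluded positives than among positives overall. With the figures above and sensitivity 0.88, that threshold is 47.5/198 = 24%. In the last row, 5.4 of 22.9 excluded youth are cases (23.6%), just below it. If positives instead followed the quoted PQ-B specificity of 0.68, there would be 47.5 + 0.32 × 1,746 = 606 of them, and the threshold would be 47.5/606 = 8%. The documents do not give the actual share.

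**5. Effect of the frame (illustration).** System prevalence = s × JID + (1 − s) × other, with the JID at 3% and the rest assumed at 1% to 8%.

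- s = 2/3: 2.33% to 4.67%.
- s = 900/2,634 = 34%: 1.68% to 6.29%.

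The two shares measure different things. The 34% divides a minimum count of screens by all court juveniles in 2016, some of whom may have passed through JID intake earlier. Neither share comes with a prevalence for the remainder, so no correction can be derived.

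**The case against.** A reader might infer that full-threshold psychosis is shown to be under-counted. The documents do not support that. The exclusion is for imminent risk from severe symptoms of any kind, not only psychosis. Removing non-cases pushes the estimate up, and step 4 shows that the net direction can reverse. The sentence on emergency care is background on usual practice and gives no count.

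A reader might also multiply the cited 3% by 900 to get 27 cases a year and then state a number missing. The title of the source for the 3% in the reference list refers to detention and correctional facilities, whereas this study covers non-incarcerated youth. The share of cases excluded is unknown as well. Such counts are illustrations only.

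Nor are these rates planning inputs for the larger trial. Aim 3B lists the SIPS standard deviation, the pre-post correlation and R² for that purpose. Prevalence and duration are descriptive goals.

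The shifts in step 3 are also modest beside sampling error: one case among the screen-negatives moves the estimate by 22.9/1,800 = 1.3 points, or 11.4/1,800 = 0.6 points with the larger comparison sample.

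Finally, the focus on non-incarcerated youth is openly declared, Participants has no first-offence criterion, and the background says most, not all, are diverted. If the population phrase was meant as JID intakes, the frame point is one of wording. The acute-exclusion point remains under either reading, because those youth are screened at the JID and then lost to the estimate.

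**Conclusion.** The plan claims a generalizability that its design does not have. Weights based on screening results alone cannot represent hospital-level exclusions or youth outside JID intake, and nothing elsewhere in the plan repairs this. That conclusion follows from the text and needs no numerical assumption.

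A downward bias in full-threshold prevalence is probable, given the emergency route for floridly psychotic youth, but it is not established and its size cannot be derived. The deviations in step 3, from about 1.3 points low to nil, depend on the borrowed 3% rate and on assumed exclusion fractions. For Aim 1B, the most acute cases may be missing; neither direction nor size can be given.

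**What to change.** 1. In Aim 1A and in the Data Analysis Plan (Aim 1), replace the target "so that our results are generalizable back to the population of JJS youth" with study-eligible youth screened at JID intake: ages 12–17, English-speaking, without an excluding developmental delay and without a need for hospital-level care.

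2. Keep a de-identified count, by phase and screen result, of youth excluded for hospital-level care. Remove them from the stratum totals so that their weight does not pass to the included youth. Report weighted prevalence for eligible youth as the main figure. Add sensitivity bounds for screened JID youth that count the excluded as none, then all, full-threshold cases. Use recorded psychosis status to narrow the bounds only where permissions allow, since the plan ties court and treatment records to consent and these youth are not enrolled.

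The cost is a narrower claim, a range in place of a point, and a small tallying task alongside the daily review of screening forms. The upper bound may be wide: if 1% of screened youth were excluded (an assumption), it would lie one percentage point above the lower bound. No care pathway changes.
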